2.2.8.1. To understand the use of immunosuppression in some subjects with complete DiGeorge anomaly, it is important to appreciate the clinical and immunological presentation of atypical complete DiGeorge anomaly ([name] et al 2004a). The word "atypical" refers to the development of rash characterized by infiltration of T cells in the skin. The pathologic diagnosis of the skin is usually spongiotic dermatitis. The rash can be a serious problem. It can clinically resemble severe atopic dermatitis. The rash is associated with oligoclonal T cells in the blood.

Lymphadenopathy develops at some point after the rash develops. If biopsied, the nodes are characterized as having dermatopathic lymphadenopathy.

Oligoclonal T cells may also infiltrate the liver as well as the skin and gut

resulting in elevations of liver enzymes, hepatomegaly, and diarrhea respectively.

The oligoclonal T cells have the phenotype of activated T cells with high expression of CD69, CD71, HLA-DR, and/or CD25. The numbers of T cells can rise to over 50,000/mm³. The T cell proliferative response to phytohemagglutinin (PHA) can rise to over 100,000 counts per minute (cpm). Clinical experience has shown that the longer these T cells are allowed to expand without suppression, the more difficult they are to suppress.

2.2.8.2. In the conduct of clinical protocol 884 (eIRB Pro00013734), it became clear that there was a great variability in the types and activation of T cells in the subjects being managed under this protocol.

2.2.8.2.1. The use of pre-transplantation rabbit anti-thymocyte globulin alone was insufficient to suppress the oligoclonal T cells found in atypical DiGeorge anomaly subjects.

2.2.8.2.2. If only pre-transplantation rabbit anti-thymocyte globulin (RATGAM) was used, the oligoclonal T cell caused pre- and post-transplantation morbidity (rash, hepatomegaly, and diarrhea). In addition, pre-transplantation cyclosporine helped decrease morbidity of the RATGAM by suppressing activated T cells.

2.2.8.2.3. For two subjects, very high levels of activated T cells remained after treatment with rabbit anti-thymocyte globulin, pre-transplantation cyclosporine and steroids. These two subjects were given anti-CD25 (daclizumab) prior to transplantation.

- Daclizumab decreased the numbers of oligoclonal activated T cells.

2.2.8.2.3.1. In one of these two subjects, persistent activated T cells were treated with a course of post-transplantation mycophenolate mofetil (MMF).

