6.2.1.8.6.1.3. After returning to the care of the local immunologist and/or referring physician, physical examinations will be requested to be done monthly for the first year after transplantation.

6.2.1.8.6.1.4. If the subject is on cyclosporine, the blood pressure should be monitored every 2 weeks, or as medically indicated, until the cyclosporine is weaned.

6.2.1.9. Infections.

6.2.1.9.1. Monitoring for Infections.

6.2.1.9.1.1. While at Duke, this is done from the time of enrollment until discharge.

6.2.1.9.1.2. After discharge, information is requested from the local immunologist/referring physician and/or parent(s) by telephone or email at the following intervals after transplantation.

- Month 3 ± 1 month
- Month 6 ± 1 month
- Month 12 ± 2 months
- Month 24 ± 2 months
- As medically indicated.

6.2.1.9.2. Recording of Infections.

6.2.1.9.2.1. The definitions are taken directly from the Blood and Marrow Transplant Clinical Trials Network

https://web.emmes.com/study/bmt2/public/Definition/Definitions_of_Inf_Severity.pdf All adverse events are to be reported as described in Section 8.3.

6.2.1.10. Possible additional biopsies. Note: These will not be done if the subject is not medically stable.

6.3. Concomitant Therapy - all of the below therapies are permitted.

6.3.1. Other procedures for medical care of research subject.

6.3.1.1. Protective Isolation: DUHS and Clinical Care Unit policies and procedures are followed while at DUMC.

6.3.1.1.1. Discontinuation of protective isolation is recommended when the subject meets criteria for permanent discontinuation of IVIG (see section 6.3.1.2.4) and/or discontinuation of PJP prophylaxis (see section 6.3.1.3.3).

6.3.1.2. Immunoglobulin Replacement Therapy.

6.3.1.2.1. Dosing.

- Immunoglobulin replacement is given to maintain IgG at ≥ 800 mg/dL.
- Intravenous immunoglobulin (IVIG) replacement monthly or
- Subcutaneous immunoglobulin replacement weekly to biweekly

6.3.1.2.2. Replacement therapy frequency depends on the subjects' IgG levels. It may be given more frequently if indicated clinically.

- If the IgG levels drops below 800 mg/dl, give replacement therapy

6.3.1.2.3. Guidelines for *initial* discontinuation of Immunoglobulin Replacement.

- Subject is not on immunosuppression
- Subject is at least 9 months post transplantation
- PHA response is $> 100,000$ cpm
- Normal serum IgA is desirable but not required

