6.3.1.2.4. Guidelines for *permanent* discontinuation of Immunoglobulin Replacement.

6.3.1.2.4.1. Two months after stopping immunoglobulin, the IgG trough level will be checked by the local immunologist and/or referring physician.

- If the IgG trough level is in the normal range for age, the subject may remain off immunoglobulin.
- If the IgG level is lower than the normal range for age, the subject will restart immunoglobulin.
 - The subject will continue on immunoglobulin for a year and then be retested by the local immunologist/referring physician using the above guidelines. Recommendations will be sent to the local/referring physician.

6.3.1.3. *Pneumocystis jiroveci* pneumonia (PJP) prophylaxis.

6.3.1.3.1. Subjects are maintained on PJP prophylaxis before and after transplantation.

6.3.1.3.2. PJP Prophylaxis.

- Septra/Bactrim – 2.5 mg trimethoprim (TMP)/kg twice a day, three days a week, usually Monday, Wednesday, Friday.
- Alternatively, Pentamidine 4 mg/kg IV every 4 weeks.

6.3.1.3.3. Guidelines for discontinuation of PJP prophylaxis.

- Subject is not on immunosuppression
- Subject is at least 9 months post transplantation
- PHA response is $>100,000$ cpm
- CD4+ count is $>200/\text{mm}^3$

6.3.1.4. Other Immunizations.

6.3.1.4.1. No live vaccinations are administered until the recipient has received killed vaccinations.

6.3.1.5. Steroid Treatment.

6.3.1.5.1. Methylprednisolone or prednisolone 1 to 2 mg/kg/d (followed by a slow taper) may be required for extreme elevations of eosinophil counts ($>30,000/\text{mm}^3$) or IgE levels $>10,000$, or pulmonary deterioration. Evidence of EBV or CMV infection should be sought for IgE levels $>500/\text{mm}^3$.

6.3.1.5.2. Methylprednisolone or prednisolone 1 to 2 mg/kg/d (followed by a slow taper) may be required for treatment of aggressive host T cell clones that appear after the initial steroids have been weaned. The clones may cause elevations in serum bilirubin, in pulmonary compromise, or other clinical problems.

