5 WARNINGS AND PRECAUTIONS

5.1 Infection Control and Immunoprophylaxis

Immune reconstitution sufficient to protect from infection is unlikely to develop prior to 6-12 months after treatment with RETHYMIC. Given the immunocompromised condition of athymic patients, follow infection control measures until the development of thymic function is established as measured through flow cytometry. This should include counseling patients and their caregivers on good handwashing practices and minimizing exposure to visitors. Monitor patients closely for signs of infection, including fever. If a fever develops, assess the patient by blood and other cultures and treat with antimicrobials as clinically indicated.

Patients should be maintained on immunoglobulin replacement therapy until all of the following criteria are met:

- No longer on immunosuppression (at least 10% of CD3+ T cells are naïve in phenotype).
- At least 9 months post-treatment.
- Phytohemagglutinin (PHA) response within normal limits.
- Normal serum IgA is also desirable but not required.

Two months after stopping immunoglobulin replacement therapy, the IgG trough level should be checked.

- If the IgG trough level is in the normal range for age, the patient can remain off of immunoglobulin replacement.
- If the IgG trough level is lower than the normal range for age, immunoglobulin replacement therapy should be restarted and continued for a year before being retested using the above guidelines.

Prior to and after treatment with RETHYMIC, patients should be maintained on *Pneumocystis jiroveci* pneumonia prophylaxis until all of the following criteria are met:

- No longer on immunosuppression (at least 10% of CD3+ T cells are naïve in phenotype).
- At least 9 months post-treatment.
- PHA response within normal limits.
- CD4+ T cell count > 200 cells/mm³.

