Patients with heart surgery anticipated within 4 weeks prior to, or 3 months after, the planned RETHYMIC treatment date, patients with human immunodeficiency virus (HIV) infection, and patients who were not considered good surgical candidates were excluded from study participation.

Patients in the efficacy population received RETHYMIC in a single surgical procedure at a dose of 4,900 to 24,000 mm² of RETHYMIC / recipient BSA in m². Patients were assigned to receive immunosuppressive therapy prior to and/or after treatment according to their disease phenotype and pre-RETHYMIC PHA response. [Table 2](#) summarizes the criteria used to administer immunosuppression. [Table 3](#) summarizes the specific immunosuppressant dosing used in RETHYMIC clinical studies. No patients were retreated with RETHYMIC.

Table 2: Summary of Treatment Assignment to Immunosuppression During Clinical Studies

Complete DiGeorge Anomaly Phenotype	Phytohemagglutinin (PHA) Response ¹	Immunosuppression Used During Clinical Studies with RETHYMIC
Typical	< 5,000 cpm or < 20-fold response to PHA over background	None
Typical	≥ 5,000 cpm and < 50,000 cpm or Evidence of maternal engraftment	
 ATG-R Methylprednisolone
Typical	≥ 50,000 cpm	
 ATG-R Methylprednisolone Cyclosporine²
Atypical	< 40,000 cpm on immunosuppression or < 75,000 cpm when not on immunosuppression	
 ATG-R Methylprednisolone Cyclosporine²
Atypical	≥ 40,000 cpm on immunosuppression or ≥ 75,000 cpm when not on immunosuppression or Evidence of maternal engraftment	
 ATG-R Methylprednisolone Cyclosporine² Basiliximab³ MMF⁴

Abbreviations: ATG-R: anti-thymocyte globulin [rabbit] (Thymoglobulin); cpm: counts per minute; MMF: mycophenylate mofetil; PHA: phytohemagglutinin

1. Values for PHA response are reported from Duke University Medical Center and may not be comparable to values reported at other clinical laboratories. A patient background value (cells without stimulus) of less than 5,000 cpm was required to consider PHA test results valid. A normal control value of > 75,000 cpm was also required during clinical studies.
2. If the patient could not tolerate cyclosporine due to adverse events (AEs), then the immunosuppression could have been changed to tacrolimus.

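### Protocol section 6.3.1 and Appendix C set different conditions for ending immunoglobulin, Pneumocystis prophylaxis and isolation; mainly in Groups 1 and 2, the protocol's can be met without evidence of graft function

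*Protocol*

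**What the plan says.** Protocol 6.3.1.2.3 allows immunoglobulin to be stopped initially when the child is off immunosuppression ("Subject is not on immunosuppression"), is at least 9 months past transplant, and "PHA response is $> 100,000$ cpm". Normal IgA is desirable but optional. Under 6.3.1.2.4 the stop becomes permanent if the IgG trough two months later is normal for age.

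Protocol 6.3.1.3.3 uses the same three conditions for Pneumocystis prophylaxis ("PHA response is $>100,000$ cpm") and adds a total CD4 count above 200/mm³.

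On isolation, 6.3.1.1.1 says: "Discontinuation of protective isolation is recommended when the subject meets criteria for permanent discontinuation of IVIG (see section 6.3.1.2.4) and/or discontinuation of PJP prophylaxis".

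Appendix C, section 5.1, gives parallel lists for the two treatments. Each opens with "No longer on immunosuppression (at least 10% of CD3+ T cells are naïve in phenotype" (closing bracket omitted here). Each keeps the 9 months and asks for PHA within normal limits, with no cpm figure. For infection control it says: "follow infection control measures until the development of thymic function is established as measured through flow cytometry". Appendix C, section 17, tells families that strict measures last until flow cytometry has confirmed reconstitution and the criteria for stopping both treatments are met.

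Protocol 1.5 states that the label supplements the amended protocol in lieu of an Investigator Brochure, and that three treated patients remain in follow-up. Section 6 places them under their local physicians.

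**The concern.** The two lists are built alike, so a physician holding the protocol package could take either as the rule. They differ on whether a naive T cell result matters, on how PHA is judged, and on whether one or both sets of criteria end isolation.

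The naive-cell difference matters most, because PHA and total CD4 do not by themselves show that the graft is working. On atypical disease, protocol 2.2.8.1 says: "The T cell proliferative response to phytohemagglutinin (PHA) can rise to over 100,000 counts per minute (cpm"; it also gives T cell numbers above 50,000/mm³. Section 8.1.2.4 says typical subjects can develop oligoclonal expansions after transplant. A child whose T cells are oligoclonal host cells rather than graft-derived naive cells might therefore pass the protocol's tests. What is at stake is ending infection protection in a child with no demonstrated thymic function, or two physicians reaching opposite decisions for the same child.

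**Working it through.** There is no sample size, error rate or planned figure to reproduce. The check sets the criteria side by side and applies them as written.

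| Item | Protocol 6.3.1 | Appendix C, 5.1 and 17 |
|---|---|---|
| Immunosuppression | Off | Off, with a bracketed 10% naive share of CD3 cells |
| Time since transplant | At least 9 months | At least 9 months |
| PHA | Above 100,000 cpm | Within normal limits, no cpm figure |
| CD4 (Pneumocystis prophylaxis only) | Above 200/mm³ | Above 200/mm³ |
| Naive T cells or flow cytometry | Not mentioned | 10% bracket; flow cytometry for infection control |
| Isolation / infection control ends on | Permanent immunoglobulin criteria and/or prophylaxis criteria | Flow cytometry, and the criteria for both treatments |

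*Test case:* at least 9 months past transplant, 0% naive T cells, and an oligoclonal expansion giving PHA above 100,000 cpm and CD4 above 200/mm³.

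1. **Groups 1 and 2.** Sections 4.2.2.1.2.1 and 4.2.2.2.2.2 plan no post-transplant immunosuppression, so that condition is met by default unless rescue treatment is given. The other conditions in 6.3.1.2.3 and 6.3.1.3.3 are met by assumption. Both treatments may stop under the protocol, and isolation may end by the prophylaxis route alone. By the immunoglobulin route, isolation can end with no T cell count at all: PHA, time, and then a normal IgG trough.
2. **The same child under Appendix C.** The flow-cytometry condition for infection control is not met. The immunoglobulin and prophylaxis conditions also fail if the 10% bracket is a requirement in its own right.
3. **Groups 3 and 4.** Sections 6.2.1.5.3.2.5.1 (cyclosporine) and 6.2.1.5.4.4.1 (tacrolimus) start the wean once naive T cells exceed 10% of CD3. Section 2.4.3 likewise maintains cyclosporine until naive cells are 10% of CD3 when the T cell count stays above 50/mm³. Under these rules the test child is still on a calcineurin inhibitor and fails the protocol's own condition, so the gap does not open.
4. **Exception in Groups 3 and 4.** Section 6.3.1.6.1 allows alemtuzumab in order to avoid long-term calcineurin inhibitors, and 6.3.1.6.2 allows other agents. A child taken off calcineurin inhibitors outside the wean rule, and then off all immunosuppression, is in the same position as in step 1.
5. **PHA.** Appendix C gives no numerical limit of normal, so the two PHA conditions cannot be ranked. The protocol's cut-off may be the stricter one. Appendix C, section 14, Table 2 footnote 1, warns that PHA values from the study centre may not be comparable with those of other laboratories, while protocol 6.1.3.2.4 requests local results.

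**The case against.** Several points on the other side stand.

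- **The protocol has its own 10% rule.** A reader might infer that any child without naive cells can pass 6.3.1. The wean rule blocks this in Groups 3 and 4, where high PHA from oligoclonal cells is most expected. In Groups 1 and 2, steroids given for aggressive host clones (6.3.1.5.2) would also mean the child is not off immunosuppression.
- **The bracket may be only a gloss.** It sits inside the condition on ending immunosuppression, and Appendix C's own dosing notes tie the cyclosporine wean to 10% naive cells. For a child never immunosuppressed, its force is unclear. The flow-cytometry condition does not depend on this reading.
- **Status of the texts.** The label is attached as reference information, and the 6.3.1 stopping items are headed as guidelines. Nothing expressly makes Appendix C, section 5.1, a management rule for subjects; equally, nothing says which text governs.
- **Isolation is not an exact match.** Protocol 6.3.1.1 concerns hospital policy during the stay at the centre; Appendix C speaks of infection control measures more broadly.

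Three stronger readings are tempting but unsupported:

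- **That the test case is common.** Protocol 9.1.2.3 reports 25 of 32 earlier subjects reaching 100 naive CD4/mm³, so 7/32 = 21.9% did not. That is a count, not a share of CD3: for illustration, 80 naive cells among 400 CD3 cells is 20%. Nothing links those seven to a high PHA response.
- **That PHA between 75,000 and 100,000 cpm is a defined zone of conflict.** The lower figure comes from "A normal control value of > 75,000 cpm was also required during clinical studies". It is an assay-control requirement, not a patient's limit of normal.
- **That the infection results are distorted.** The label joined the protocol only after enrolment closed, so this conflict can touch at most three subjects' data.

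**Conclusion.** The inconsistency is real and can be checked line by line, but its reach is narrow. It opens mainly in Groups 1 and 2, or where calcineurin inhibitors were stopped outside the wean rule. In those settings every written protocol condition can be met without evidence of graft function, while Appendix C would continue infection control.

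This assumes that an oligoclonal expansion after transplant can reach the PHA and CD4 thresholds in such a child. Section 2.2.8.1 gives the PHA figure for atypical disease; section 8.1.2.4 describes expansions in typical subjects but gives no PHA value. The case is therefore possible, with unknown frequency. At most three children are affected, and the documents give neither their Groups nor their current prophylaxis status. It merits correction because it bears on infection protection and the correction is cheap, not because it is shown to change any result.

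**What to change.** Reconcile protocol 6.3.1.1.1, 6.3.1.2.3, 6.3.1.2.4 and 6.3.1.3.3, the wean rules in 6.2.1.5.3.2.5 and 6.2.1.5.4.4, and Appendix C sections 5.1 and 17 into one set of conditions. That set should settle:

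- whether a naive T cell or flow-cytometry result is needed, including for a child never immunosuppressed;
- how the PHA condition is expressed when results come from different laboratories;
- whether isolation or infection control ends on one set of criteria or on both.

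State which text governs and send the single version to the local physicians of the remaining subjects. The clinical choice belongs to the sponsor and investigator.

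The cost is a short amendment and a letter. No new procedure is required: section 6.2.1.8.2.2 already schedules flow cytometry with naive T cells at months 3, 6, 9 and 12.

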5.2 Graft versus Host Disease

In clinical studies with RETHYMIC, GVHD occurred in 11 (10%) RETHYMIC-treated patients of whom 6 (55%) died. RETHYMIC may cause or exacerbate pre-existing GVHD. Seven patients (7%) experienced autologous GVHD, 3 patients (3%) experienced GVHD due to maternal cells and 1 patient (1%) experienced GVHD due to cells from a prior hematopoietic cell transplant (HCT). Risk factors for GVHD include atypical complete DiGeorge anomaly phenotype, prior HCT and maternal engraftment. GVHD may manifest as fever, rash, lymphadenopathy, elevated bilirubin and liver enzymes, enteritis, and/or diarrhea. Patients with elevated baseline T cell proliferative response to PHA > 5,000 cpm or > 20-fold over background should receive immunosuppressive therapies to decrease the risk of GVHD (Table 2 and Table 3). Development of GVHD symptoms should be closely monitored and promptly treated.

5.3 Autoimmune Disorders

Thirty-seven patients (35%) in the RETHYMIC clinical program experienced autoimmune-related adverse reactions. These events included: thrombocytopenia (including idiopathic thrombocytopenic purpura) in 13 patients (12%), neutropenia in 9 patients (9%), proteinuria in 7 patients (7%), hemolytic anemia in 7 patients (7%), alopecia in 4 patients (4%), hypothyroidism in 2 patients (2%), autoimmune hepatitis in 2 patients (2%), and autoimmune arthritis (juvenile idiopathic and psoriatic arthritis) in 2 patients (2%). One patient (1%) each experienced transverse myelitis, albinism, hyperthyroidism, and ovarian failure. The onset of autoimmune related events ranged from the three days before the surgical implantation procedure until 16 years post-treatment. Most events occurred within the first year after treatment.

Monitor complete blood counts with differential weekly for the first 2 months post-treatment and then monthly through 12 months post-treatment. Liver enzymes including aspartate aminotransferase and alanine aminotransferase, serum creatinine levels, and urinalysis should be performed monthly for 3 months and then every 3 months through 12 months post-treatment. Thyroid function studies should be performed prior to treatment and then at 6 months and 12 months post-treatment. After 12 months, testing should be performed annually.

5.4 Renal Impairment

Ten patients with renal impairment (elevated serum creatinine at baseline) were treated in studies with RETHYMIC. Five of these patients died within 1 year and a sixth patient died 3 years after treatment with RETHYMIC. Renal impairment at baseline is considered a risk factor for death.

5.5 Cytomegalovirus Infection

In clinical studies with RETHYMIC, 3 out of 4 patients with preexisting CMV infection prior to treatment with RETHYMIC died. The benefits/risks of treatment should be considered prior to treating patients with pre-existing CMV infection.

5.6 Malignancy

Because of the underlying immune deficiency, patients who receive RETHYMIC may be at risk of developing post-treatment lymphoproliferative disorder (blood cancer). The infant tissue donor is screened for Epstein-Barr virus (EBV) and cytomegalovirus (CMV), but patients should be tested for EBV and CMV using PCR prior to and 3 months following treatment with RETHYMIC, or after any exposure to or suspected infection with CMV or EBV.

5.7 Transmission of Serious Infections and Transmissible Infectious Diseases

Transmission of infectious disease may occur because RETHYMIC is derived from human tissue. Disease may be caused by known or unknown infectious agents. Donors are screened for increased risk of infection with human immunodeficiency virus (HIV), human T-cell lymphotropic virus (HTLV), hepatitis B virus (HBV), hepatitis C virus (HCV), *Treponema pallidum*, *Trypanosoma cruzi*, West Nile virus (WNV), transmissible spongiform encephalopathy (TSE) agents, vaccinia and Zika virus. Donors are also screened for clinical evidence of sepsis, and communicable disease risks associated with xenotransplantation. Blood samples (from the infant tissue donor or the birth mother, as applicable) are tested for HIV types 1, 2, and O, HTLV types I and II, HBV, HCV, *T. pallidum*, WNV, and *T. cruzi*. Blood from the infant tissue donor is also tested for *Toxoplasma gondii*, Epstein-Barr virus (EBV) and CMV. RETHYMIC is tested for sterility, endotoxin, and mycoplasma. These measures do not eliminate the risk of transmitting these or other infectious diseases and disease agents.

Testing of maternal and infant donor blood is also performed for evidence of donor infection due to cytomegalovirus (CMV).

Product manufacturing includes porcine- and bovine-derived reagents. While all animal-derived reagents are tested for animal viruses, bacteria, fungi, and mycoplasma before use, these measures do not eliminate the risk of transmitting these or other transmissible infectious diseases and disease agents.

Final sterility and mycoplasma test results are not available at the time of use, but manufacturing personnel will communicate any positive results from sterility testing to the physician. Report the occurrence of transmitted infection to Enzyvant at [contact].

